2 SCHEDULE OF ASSESSMENTS AND PROCEDURES

[figure not shown]
CONFIDENTIAL

CONFIDENTIAL

Table 2.2 Schedule of assessments and procedures- Part B

CONFIDENTIAL

CONFIDENTIAL

Table 2.3 Pharmacokinetic Sampling Schedule – Part A

Visit	Study Day	Time Relative to 1 st Study Drug Administration (Hour)	Pharmacokinetic Blood Sample
0	-28 to -1	Not applicable	Not applicable
1	1	0 (predose)	X
2	3	48 ± 4 (trough)	X
3	6	120 ± 4 (trough)	X
4	8	168 ± 4 (trough)	X
5	15	336 ± 4 (trough)	X
6	22	504 ± 4 (trough)	X
7	29	672 ± 4 (trough)	X
8	36	Not applicable	Not applicable

Pharmacokinetic samples will be collected as close to the nominal time point as possible. Allowable windows for PK collection will be ± 4 hours for all trough samples.

LIST OF ABBREVIATIONS

Abbreviation	Definition
UP	uremic pruritus
AE	adverse event
BLQ	below the limit of quantification
BMI	body mass index
BUN	blood urea nitrogen
CFR	Code of Federal Regulations
CNS	central nervous system
CRU	clinical research unit
CRO	contract research organization
C _{trough}	lowest observed blood concentration prior to next application
DSMB	data and safety monitoring board
eCRF	electronic case report form
EOS	end-of-study
FDA	Food and Drug Administration
FU	follow-up
GCP	Good Clinical Practice
HBV	hepatitis B virus
HCV	hepatitis C virus
HIV	human immunodeficiency virus
ICF	informed consent form
ICH	International Council for Harmonisation
IEC	independent ethics committee
IRB	institutional review board
Itch NRS	itch numerical rating scale
NOAEL	no observed adverse effect limit
NRS	numerical rating scale
MedDRA	Medical Dictionary for Regulatory Activities
OTC	over-the-counter
PK	pharmacokinetic(s)
SAE	serious adverse event
SAS	safety analysis set
SD	standard deviation
SOP	standard operating procedure
SRM	study reference manual
ULN	upper limit of normal

CONFIDENTIAL

STUDY ADMINISTRATIVE STRUCTURE

Sponsor:

Lumosa Therapeutics Co., Ltd.

CONFIDENTIAL

[REDACTED]
[REDACTED].

3.5 Hypotheses

The study is to determine the safety, local tolerance, PK, and explore the potential efficacy of 4-week (Part A) and the safety and efficacy of 8-week (Part B) multiple dermal applications of LT5001 drug product in the hemodialysis patients with moderate to severe UP.

4 OBJECTIVES

4.1 Primary Objective – Part A

- To investigate the safety, local tolerability, and PK of 4-week, multiple dermal applications of LT5001 drug product to hemodialysis patients with UP.

4.2 Primary Objective – Part B

- To investigate the safety and efficacy of 8-week, multiple dermal applications of LT5001 drug product to hemodialysis patients with UP.

5 STUDY DESIGN

5.1 Study Design and Overview

This study contains 2 parts. Both study parts will include hemodialysis patients with moderate to severe UP. Part A will assess the safety, tolerability, and PK of LT5001 drug product with 4-week of daily BID topical dosing. Part B will assess safety and efficacy with 8-week of daily topical dosing. The maximum daily dose and recommended regimen for Part B will depend on DSMB comments.

Part A:

Part A will be a randomized, double-blind, and placebo-controlled. It will enroll 18 patients between 20 to 75 years of age, inclusive.

After providing written informed consent, each patient will be evaluated for study eligibility within 28 days of Day 1. During this period, patient need to daily record the worst itch NRS in the patient diary for 7 days (diary run-in). At least 6 of 7 daily Worst Itching Intensity NRS worksheet must be completed and mean NRS score > 4 to qualify. At screening, physical examination of the skin will be conducted as a full-body skin assessment, which will serve as subject's baseline skin condition. Photographs of the treatment area may be considered under the investigator's judgment (optional). Patient's baseline skin condition will be used as reference for comparison in the application site examination from Visit 2 to 8 in Part A. After signing the informed consent, patients may continue previous antipruritic therapy throughout the study prescribed by the physician (unless specified in the prohibited medication [Section 7.7.3](#)). The dosing regimen of the previous antipruritic therapy cannot be changed. Gabapentin, pregabalin, topical antihistamine/ corticosteroid agents, OTC antihistamine/ corticosteroid agents are prohibited throughout the study. Eligible patients will be randomized into 2 groups (LT5001 drug product and Placebo) at a ratio of 2:1. [REDACTED]

[REDACTED]
Topical dosing will occur for 4 weeks, consisting of 56 total doses throughout the treatment period. Patient will be instructed to directly apply the study drug to the itch area. A fingertip unit of study drug is recommended to treat an area of skin twice the size of an adult palm.

In the first 7 days of study treatment, patient will also need undergo a 7-day repeated open application tests (ROAT). A 0.5 fingertip unit of the study drug is recommended to apply to a 5x5 cm² fixed pre-marked zone without any skin lesions near the antecubital fossa twice daily in the morning and evening for 7 days. If skin lesion is occurred in the antecubital fossa, it is acceptable to choose the volar forearm or ventral inner arm without skin lesion under the judgment of investigator to perform ROAT (avoid the area depicted in the [Section 7.2 Treatments Administered](#)). Patients will need to daily assess the itch condition at a fixed period by themselves and record in the patient diary including the daily 24-hour worst itch NRS,

application time/ site of the study drug, time and intensity of the itch between the morning and evening dose and return the diary at every visit.

Patients will visit the CRU for dosing on Day 1, and for procedures including clinical laboratory test samplings, physical examinations, vital sign assessments, itch assessment (Skindex-10 and 5D-itch scale), and application site assessments by ICDRG scale (dermatitis, pruritus, paresthesia, erythema, dryness, vesicles, irritation, papules, burning) according to [Table 8.2](#), and PK blood samples will be performed according to Table 2.3. Application site evaluation will be conducted in each visit (Visit 2 to 8) in Part A. Photographs of the application site may be considered under the investigator's judgment (optional). Baseline skin condition performed at screening will be used as reference for comparison.

Patient will need to return the study drug during 3 times per week following his/her dialysis schedule. The actual dosing in each patient will be determined by subtract the weight of each returned study drug from the initial weight (T_0).

Patients will return for a follow-up visit to complete safety evaluations according to [Table 2.1](#). Application site assessments (dermatitis, pruritus, paresthesia, erythema, dryness, vesicles, irritation, papules, burning) by ICDRG scale according to Table 8.2, AEs, and concomitant medications and procedures will be recorded.

Part B:

Part B will be randomized, double-blind, and placebo-controlled. It will enroll 90 patients between 20 to 75 years of age, inclusive.

After providing written informed consent, each patient will be evaluated for study eligibility during screening (within 28 days of Day 1). During this period, patient need to daily record the worst itch NRS in the patient diary for 7 days (diary run-in). At least 6 of 7 daily Worst Itching Intensity NRS worksheet must be completed and mean NRS score > 4 to qualify. At screening, physical examination of the skin will be conducted as a full-body skin assessment, which will serve as subject's baseline skin condition. Photographs of the treatment area may be considered under the investigator's judgment (optional). Patient's baseline skin condition will be used as reference for comparison in the application site examination from Visit 2 to 9 in Part B.

After signing the informed consent, patients may continue all previous antipruritic therapy prescribed by the physician throughout the study (unless specified in the prohibited medication [Section 7.7.3](#)). The dosing regimen of the previous antipruritic therapy cannot be changed. Gabapentin, pregabalin, topical antihistamine/ corticosteroid agents, OTC antihistamine/ corticosteroid agents are prohibited throughout the study. Eligible patients will be randomized into 2 groups (LT5001 drug product and Placebo) at a ratio of 1:1. Topical dosing will occur for 8 weeks. [REDACTED]

[REDACTED] Topical dosing will occur for 8 weeks. Patients will need to daily assess the

itch condition at a fixed period by themselves and record in the patient diary including the daily 24-hour worst itch NRS, application site/ time of the study drug, time and intensity of the itch between the morning and evening dose, and return the diary every visit.

Patients will visit the CRU for dosing on Day 1 and procedures including clinical laboratory test sampling, physical examinations, vital sign assessments, and itch assessment (Skindex-10 and 5D-itch scale), and application site assessments (dermatitis, pruritus, paresthesia, erythema, dryness, vesicles, irritation, papules, burning) by ICDRG scale according to Table 8.2, AEs, and concomitant medications and procedures will be performed according to [Table 2.2](#). Application site evaluation will be conducted in each visit (Visit 2 to 9) in Part B. Photographs of the application site may be considered under the investigator's judgment (optional). Baseline skin condition performed at screening will be used as reference for comparison.

Patient will need to return the study drug during 3 times per week following his/her dialysis schedule. The actual dosing in each patient will be determined by subtract the weight of each returned study drug and subtract from the initial weight (T_0).

[figure not shown]

Figure 5.1 Study Design Schematic (Part A)

[figure not shown]

Figure 5.2 Study Design Schematic (Part B)

5.1.1 Interim Safety/ Pharmacokinetic Data Review

Subject will receive application site examination at each visit (Part A: Visit 2 to 8; Part B: Visit 2 to 9) assessed by the trained study team, using ICDRG scale. If subject experience a new or worsening localized skin reaction in the treatment area, the subject should report to the study coordinator and/or investigator during the visit. Baseline skin condition conducted at screening in the physical examination should be used as a reference for comparison. All AEs should be recorded in the eCRF

If a subject experience 1 newly arise acute inflammation of the skin (e.g. pain, transient erythema, vesiculation, severe swelling with bullae, ulceration, or even both) at the application site, and is related (at least possible) with study drug, study treatment is recommended to be interrupted. Upon resolution of the acute inflammation, subject may resume study treatment upon investigator's judgment.

After completion of 18 subjects in Part A, the DSMB will convene to review all safety and PK data. Part B will only occur if the DSMB determines that the current dose was safe and well-tolerated. Doses for Part B will be decided by the DSMB after their review of the cumulative safety data targeted for review (AEs, vital signs, clinical laboratory results, physical examination results, itch results, and application site examination results) and available PK data from Part A. Sponsor will make the final decision in an unblinded fashion.

An ad hoc DSMB meeting will be convened in the following situations:

1. In the event of 4 subjects experiencing drug related (at least possible) adverse events with at least moderate intensity after the 1st dose of study drug or any ICDRG grade of ROAT $\geq 1+$ found during the first 7 days of study treatment, ad hoc DSMB meeting will be held to review the safety data and recommend in writing to Sponsor whether to continue, modify, or stop the clinical study on the basis of safety considerations.

2. In the event of ≥ 2 subjects experiencing drug related (at least possible) adverse events with at least moderate intensity in the first 6 subjects receiving study drug after the 1st dose or any ICDRG grade of ROAT $\geq 1+$ found during the first 7 days of study treatment, ad hoc DSMB meeting will also be convened to discuss the safety events to recommend Sponsor whether to continue, modify, or suspension the enrollment of the study.

DSMB members will include experts in the disease under study and biostatistics who are not participating in this study and do not have affiliation with the Investigators or the Sponsor. Full details of the role, remit and membership of the DSMB will be detailed in a separate DSMB Charter

5.1.2 Duration of Study

Part A:

Patient participation is expected to last up to 63 days, including a 28-day screening period (consisting of a 7-day diary run-in to build baseline itch NRS) and a 36-day on study period (consisting of 56 total doses from Day 1 to Day 29, and a 7 day follow-up/EOS visit at Day 36).

Part B:

Patient participation is expected to last up to 85 days, including a 28-day screening period (consisting of a 7-day diary run-in to build baseline itch NRS) and a 57-day on study treatment period.

5.1.3 Definition of Study Completion

End-of-study procedures will be performed as specified in the schedules of assessments ([Table 2.1](#) and [Table 2.2](#)); patients who withdraw from the study early will have EOS procedures performed at the time or within 7 days of discontinuation. Patients with ongoing clinically significant clinical or laboratory findings will be followed until the finding is resolved or medically stable; reasonable attempts will be made to follow-up with patients. The patient's participation in the study will end once all study assessments and follow-up have been completed.

5.1.4 End of Study

The end of the study is defined as the date when the last patient has completed all study procedures up to and including the EOS/early termination visit as specified in the schedules of assessments ([Table 2.1](#) and [Table 2.2](#)).

6 SELECTION AND WITHDRAWAL OF PATIENTS

Patients must meet all the following inclusion criteria and none of the exclusion criteria in order to be enrolled in this study. Prospective approval of protocol deviations to recruitment and enrollment criteria, also known as protocol waivers or exemptions, is not permitted.

6.1 Inclusion Criteria

Patients must meet all inclusion criteria to be eligible for study participation.

1. Male or female 20 to 75 years of age, inclusive, at the time of signing informed consent.
2. Patient must have been receiving in-center hemodialysis for \geq 3 months and currently on a schedule of 3 times per week.
3. Patient must have had at least 2 urea reduction ratio (URR) measurements \geq 65%, at least 2 single-pool Kt/V measurements \geq 1.2, or 1 single-pool Kt/V measurement \geq 1.2 and 1 URR measurement \geq 65% on different dialysis days within the last 3 month period prior to randomization.
4. Body weight \geq 40 kg (not to exceed 115 kg) and BMI \geq 18.0 and \leq 31.0 kg/m² at screening (after hemodialysis).
5. History of pruritus $>$ 4 weeks of duration
6. Females with childbearing potential (defined as women \leq 50 years of age with a history of amenorrhea for $<$ 12 months prior to study entry) must agree to use effective methods of contraception from screening through the last dose of study drug.
7. Males who are sexually active and whose partners are females of childbearing potential must agree to use condoms from screening through 90 days, whichever is longer, after administration of the last dose of study drug, and their partners must be willing to use a highly effective method of contraception from screening through 90 days after administration of the last dose of study drug.
8. Males must agree to not donate sperm from screening through 90 days, whichever is longer, after administration of the last dose of study drug.
9. Patient must have completed at least 6 days of Worst Itching Intensity NRS worksheets in the 7-day Diary run-in Period and have a mean Worst Itching Intensity NRS score $>$ 4 prior to randomization.
10. Patients must be able to complete questionnaires, understand the study procedures, and communicate effectively with the study personnel.

6.2 Exclusion Criteria

Patients will not be eligible for study participation if they meet any of the exclusion criteria, or will be discontinued at the discretion of the investigator in consultation with the medical monitor if they develop any of the exclusion criteria during the study.

- [REDACTED]
- [REDACTED]
- 2. History of major surgery or trauma within 12 weeks of screening in the judgement of the investigator, or surgery planned during the study.
- 3. [REDACTED]
- [REDACTED]
- [REDACTED]
- 4. Has had a significant alteration in dialysis regimen within 2 weeks of the Screening Visit or anticipated to be receiving nocturnal dialysis, home hemodialysis treatment, or kidney transplant during the study.
- 5. Has any known history of allergic reaction to opioids.
- 6. History of a latest positive serology test for HBV (HBsAg) or HCV (anti-HCV) within 1 year prior randomization consistent with current infection. Confirmatory tests will be allowed at the discretion of the investigator to rule out false positives.
- 7. Has any known history of HIV.
- 8. Positive pregnancy test or is lactating.
- 9. Has required peritoneal dialysis.
- 10. Alanine aminotransferase and/or aspartate aminotransferase concentration $> 2 \times$ the ULN, or total bilirubin $> 1.8 \times$ ULN, or hemoglobin concentration $< 9 \text{ g/dL}$ at the Screening Visit.
- 11. Has taken other investigational drugs or participated in any clinical study within 30 days or 5 half-lives (if known) of the investigational drug's PK, PD, or biological activity (if known), whichever is longer, prior to first dose of study drug in this study or is currently participating in another clinical study.
- 12. Has received a vaccination within 3 days prior to administration of the first dose of study drug.
- 13. Has pruritus probably or definitely attributed to a cause other than renal disease or its complications such as atopic dermatitis, chronic urticarial, or hepatic pruritus caused by chronic liver disease.
- 14. Presence of skin infection (as defined by the investigator) on the area to be treated.

15. Any other condition or prior therapy that, in the investigator's opinion, would make the patient unsuitable for the study, or unable or unwilling to comply with the study procedures
16. Involved in the planning or conduct of this study.
17. Unwilling or unlikely to comply with the requirements of the study.

6.3 Screen Failures

Patients who are discontinued from the study prior to study drug administration will be considered screen failures. The patient may be re-screened if the patient was not discontinued from the study due to noncompliance with the protocol, and also the investigator considers the patient suitable to participate in the study. If the patient is re-screened, the patient must be re-consented.

Screen failure data will be recorded in the eCRF.

6.4 Patient Withdrawal

Patients are free to withdraw from the study at any time, for any reason, and without prejudice to further treatment. The investigator may withdraw a patient if, in the investigator's judgment, continued participation would pose unacceptable risk to the patient or to the integrity of the study data. All procedures for early withdrawal must be completed. Reasons for withdrawal may include:

- AE
- Lost to follow-up
- Physician decision
- Pregnancy
- Protocol deviation
- Study terminated by Sponsor
- Withdrawal by patient
- Death
- Noncompliance with study drug or procedure
- Other

If patients who are withdrawn for reasons other than AEs, additional patients may be enrolled if additional data are necessary to establish safety and tolerability.

In the event of a patient's withdrawal, the investigator will promptly notify the medical monitor and will make every effort to complete the follow-up/EOS assessments. All withdrawn patients with ongoing clinically significant clinical or laboratory findings will be followed until the

finding is resolved or medically stable; reasonable attempts will be made to follow-up with patients.

6.5 Early Termination of Study

The study may be terminated at any time by the Sponsor if serious side effects occur, if potential risks to study participants are identified, if the investigator does not adhere to the protocol, or if, in the Sponsor's judgment, there are no further benefits to be achieved from the study. In the event that the clinical development of the study drug is discontinued, the Sponsor shall inform all investigators/institutions and regulatory authorities.

7 TREATMENT OF PATIENTS

7.1 Identity of Study Drugs

A description of the study drugs is presented in Table 7.1.

Table 7.1 Study Drugs

7.2 Treatments Administered

The study medication will be applied directly to the itching area as instructed by the study staff. A fingertip unit of study drug is recommended to treat an area of skin twice the size of an adult palm. In the first 7 days of study treatment, patient will also need to apply 0.5 fingertip unit of the study drug to a 5x5 cm² fixed pre-marked zone without any skin lesions near the antecubital fossa BID in the morning and evening for 7 days. If skin lesion is occurred in the antecubital fossa, it is acceptable to choose the volar forearm or ventral inner arm without skin lesion under the judgment of investigator to perform ROAT (avoid the area depicted below).

Avoid apply LT5001 drug product around the eyes, mouth, nose, mucous membrane, genital, anal region, vascular access for hemodialysis and its surrounding region (1 cm in both sides). Do not apply the study medication on to the vesicles, open wound, or on the area of erythema, rash, swelling, paresthesia, pain, desquamation, discoloration.

Part A:

LT5001 drug product will be applied BID in the morning and evening per the schedule of assessment in Table [REDACTED]

Part B:

The dosing regimen will adjust according to DSMB suggestion after Part A completion. If DSMB has no comment for frequency of treatment administration, the dosing regimen will be kept the same as Part A. [REDACTED]

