8.1 Diary run-in (7-days itch NRS)

Subject need to record the daily worst itching intensity NRS for 7 days in the patient diary at screening. At least 6 of 7 itch NRS must be completed and the mean NRS score > 4 to be qualified for participation in the study.

After signing informed consent, a patient diary will be provided to the subject for the Diary run-in procedure at screening. Patient eligibility will be confirmed after completion the study procedures specified in the schedule of assessment. In practice, the order of the procedures should be: (1) obtain informed consent (2) review inclusion and exclusion criteria (3) Diary run-in and all other assessments for screening indicated in the schedule of assessments ([Table 2.1](#), [Table 2.2](#)) (4) confirm eligibility (5) randomization.

8.2 7-days Repeated open application tests (7-days ROAT)

In the first 7 days of study treatment, subject will need to undergo a 7-day repeated open application tests (ROAT). A 0.5 fingertip unit of the study drug is recommended to apply to a $5 \times 5 \text{ cm}^2$ fixed pre-marked zone without any skin lesions near the antecubital fossa twice daily in the morning and evening for 7 days. If skin lesion is occurred in the antecubital fossa, it is acceptable to choose the volar forearm or ventral inner arm without skin lesion under the judgment of investigator to perform ROAT (avoid the area depicted in the Section 7.2 Treatments Administered).

During the 7-days ROAT, the pre-marked zone applied with the study drug will be examined and assessed by ICDRG scale in each visit (details in [Section 8.8.6 Application Site Examination](#)). In the event of ICDRG $\geq +$ that is considered clinically significant will be recorded as AE. The investigator may photograph the skin condition if the investigator considered helpful for the safety assessment in the DSMB meeting (optional).

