8.8.6 Application Site Examination

Application Site Examination will be conducted at Visit 2 to 8 in Part A and Visit 2 to 9 in Part B as indicated in schedule of assessment ([Table 2.1](#), [Table 2.2](#)). Application site evaluation will be conducted by comparing the skin of the application site with the baseline skin condition in each visit.

The application site evaluation will include dermatitis, pruritus, paresthesia, erythema, dryness, vesicles, irritation, papules, burning assessed by ICDRG scale (Table 8.2). An abnormal application site finding that is considered clinically significant will be recorded as AE. The investigator may consider photograph the skin condition under the consent of the subject if the investigator considered helpful for the safety assessment in the DSMB meeting (optional).

Table 8.2 Grading score by International Contact Dermatitis Research Group (ICDRG)

Grading	Morphology	Interpretation
-	No reaction	Negative
±?	Erythema only, no infiltration	Doubtful reaction
+	Erythema, infiltration, possibly discrete papules	Weak positive reaction
++	Erythema, infiltration, papules, vesicles	Strong positive reaction
+++	Erythema, infiltration, confluent vesicles	Extreme positive reactions
Ir	Different types of reactions (dermatitis, paresthesia, dryness, burning)	Irritant reaction

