11.6 Application site examination

The application site evaluation will include dermatitis, pruritus, paresthesia, erythema, dryness, vesicles, irritation, papules, burning assessed by ICDRG scale. ICDRG scale consist of negative(-), doubtful reaction(+/?), weak positive reaction(+), strong positive reaction(++) , extreme positive reactions(+++), irritant reaction (IR). Application site examination (observed and change from baseline) will be summarized as number and percentage of subjects by each treatment group.

7-days ROAT assessed by ICDRG scale will also be summarized as number and percentage of subjects by each treatment group

12 Pharmacokinetics

Pharmacokinetics analysis will be performed only in Part A.

Pharmacokinetic parameters will be listed by subject and treatment using the pharmacokinetic analysis set (PKAS)

All calculations for PK parameters will be based on actual dosing and sampling times recorded during the study. Considering the actual dose received by each patient may vary, the PK parameter will be adjusted by dividing to the actual dose of each patient.

QMS Document Name: Statistical Analysis Plan	Page 22 of 33
QMS No (include version ref): STF-015-GL.02	Document date: 09JUL2019
CONFIDENTIAL	

Blood concentrations that are below the limit of quantification (BLQ) prior to the first measurable concentration will be set to zero, BLQ values that are between measurable concentrations will be set to missing, and BLQ values that occur at the end of the profile (after the last quantifiable concentration) will be set to missing.

All PK parameters will be summarized as descriptive statistics (n, arithmetic mean, standard deviation (SD), CV%, minimum, median, and maximum, geometric mean, and geometric CV%). Missing values will be omitted from the calculation of descriptive statistics

Scatter plots of individual adjusted PK parameters ($C_{trough}/$ Actual Dose) and non-adjusted PK parameters (C_{trough}) versus time for LT5001 drug product will be produced on log-log scales using the PKAS.

13 Interim Analyses

Interim analysis and DSMB:

After Part A completion, the interim analysis for all data will be done.

Statistical analysis for interim analysis will be performed based on this SAP.

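### The protocol does not say what happens to the 7-day ROAT once the test zone turns red, and the SAP cannot show that a ROAT was cut short

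*Protocol*

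**What the plan says.** - **The course.** Protocol 7.2 and 8.2 have the patient apply study drug to a "fixed pre-marked zone without any skin lesions near the antecubital fossa BID in the morning and evening for 7 days". The synopsis, Protocol 5.1 and SAP 3.1 repeat this.
- **The ban.** The next paragraph of Protocol 7.2 reads: "Do not apply the study medication on to the vesicles, open wound, or on the area of erythema, rash, swelling, paresthesia, pain, desquamation, discoloration". It states no exception for the ROAT zone.
- **The interruption.** Protocol 5.1.1 covers a new acute inflammation at the application site that is at least possibly related, with transient erythema among its examples. In that case "study treatment is recommended to be interrupted", and treatment may resume at the investigator's discretion.
- **The grades.** In Table 8.2, '±?' (doubtful) is "Erythema only, no infiltration" and '+' (weak positive) is "Erythema, infiltration, possibly discrete papules".
- **What '+' does.** Protocol 8.2 records a ROAT grade of '+' or higher as an AE if clinically significant. Protocol 5.1.1 and SAP 1.2 list a ROAT grade of at least '1+' in the first 7 days as a ground for an ad hoc DSMB meeting.
- **The analysis.** SAP 11.6: "7-days ROAT assessed by ICDRG scale will also be summarized as number and percentage of subjects by each treatment group". It mentions neither the number of applications nor early stopping.

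**The concern.** The ROAT is the trial's dedicated test of local tolerance, and it works by repeated exposure of one patch of skin. The ban in 7.2 takes effect when that patch begins to react. If it is followed, the challenge is shortened in exactly the patients who show a reaction. If the 7-day instruction is followed, it is not. Patients or staff who act on different passages would deliver different challenges under the same test name.

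The result feeds decisions. '+' is the level at which the ROAT itself leads to an AE record or an ad hoc DSMB review, and application-site findings are part of what the DSMB weighs before Part B. Shortened exposure would tend to lower the grades reached, and nothing in the planned ROAT table would reveal it.

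**Working it through.** The plan gives no figure to reproduce. The check is a cross-reading, with a little arithmetic on exposure.

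**1. Planned exposure.** 2 applications per day × 7 days = 14.

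**2. Exposure at the readings.** Protocol 8.2 has the zone graded at each visit. Table 2.3 puts the visits in this period at 48, 120 and 168 hours (Days 3, 6 and 8). Assume the first application is at hour 0, applications are 12 hours apart, and each visit precedes the next application (Table 2.3 labels these samples as troughs):
- Day 3: 48/12 = 4 applications; 4/14 = 29%.
- Day 6: 120/12 = 10 applications; 10/14 = 71%.
- Day 8: 168/12 = 14 applications; 100%.

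Most applications therefore fall between readings, so a zone can be stopped without a grade being taken at that moment.

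**3. What each passage implies when the zone reddens.**
- The 7-day instruction in 7.2 and 8.2: continue to application 14.
- The ban in 7.2: no further application on that skin.
- Section 5.1.1: interruption is recommended, but the text does not say whether this means the zone, the itch area or all treatment.

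No readable passage says which of these governs the ROAT zone.

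**4. The ban against the grading scale.** Erythema is part of '±?', '+', '++' and '+++'. Vesicles, also on the banned list, are part of '++' and '+++'. Paresthesia, also banned, is listed under 'Ir'. The ban therefore reaches every grade above negative, and under it application would end at '±?' if that is what appears first.

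**5. What the reported data could show.**
- SAP 11.6 gives number and percentage by grade. A '±?' reached after 4 applications and a '±?' reached after 14 fall in the same cell.
- SAP 8.4 derives compliance from morning and evening tube use and does not separate the ROAT zone from the itch area.
- Protocol 8.6.1 has the diary record the time and site of application, and SAP 8 plans a listing of administration dates and times. The raw material for spotting an early stop may exist, but no summary uses it.

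**6. Size.** Neither document gives a reaction rate, so no expected effect can be computed. As an illustration only, one of the 12 LT5001 patients in Part A is 1/12 = 8.3%.

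**7. Where the differences would arise.** SAP 5.1 gives Part A one site, so in Part A they would be between patients or staff rather than between sites.

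**The case against.** The strongest reply is that the list in 7.2 only guides the choice of where to apply. Protocol 8.2 supports this, because it cites the list for picking the ROAT site ("avoid the area depicted in the Section 7.2 Treatments Administered"). That reading is possible. But the sentence is worded as a general ban on application, and the zone must already be free of lesions when chosen. The text does not settle the matter.

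Second, 5.1.1 only recommends, and a planned course with a discretionary safety interruption is not in itself a contradiction. That stands. The conflict is between the 7-day instruction and the unqualified ban; 5.1.1 adds an unstated scope.

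Third, reactions have other routes into the data. Section 8.8.6 records any clinically significant application-site finding as an AE, with no minimum grade. The AE form captures interruption or withdrawal of drug. Related AEs of at least moderate intensity count towards an ad hoc meeting, and the DSMB sees application-site results after Part A. These routes are real but not equivalent. A faint red patch may be neither clinically significant nor moderate, which under 9.2.2 means interference with usual activity or a need for specific treatment.

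Three stronger readings are tempting, and the documents do not support them:
- A reader might infer that '+' can never be reached. Zones are graded at visits, so one may already be '+' at first reading. Nothing says that a reaction must pass through '±?' or cannot progress after application stops, and the trigger counts a grade found in the first 7 days whether or not dosing continued.
- A reader might infer that a reacting zone could be exchanged for fresh skin, since another arm area is allowed if the fossa has a lesion and no timing is given. The zone is called fixed and pre-marked, so initial choice is the natural reading.
- A reader might tie the count of two among the first six patients to ROAT grades. In 5.1.1 that count attaches to related AEs of at least moderate intensity.

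Finally, Table 2.1 is not readable in the text available and the DSMB Charter is a separate document. Either might address ROAT handling.

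**Conclusion.** The point holds as a conflict between passages together with a reporting gap. Read literally, Protocol 7.2 both requires a 7-day course on a fixed zone and forbids continuing it once erythema or paresthesia appears there. Application may then stop before '+' develops. SAP 11.6 as written cannot distinguish a ROAT stopped for a reaction from one that ran all 14 applications.

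The direction of any bias is towards fewer '+' grades. Its size is unknown: it depends on how many patients react, how many of those would have progressed with continued application, and which passage was followed. A stop at the Day 3 visit would mean about 29% of the planned exposure, given 12-hourly application from hour 0.

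The conclusion assumes that neither Table 2.1 nor the DSMB Charter already resolves the matter. It should be corrected, because the local-tolerance result cannot be interpreted cleanly without it, but it does not undermine the rest of the safety assessment.

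**What to change.** - **Protocol.** The sponsor should reconcile 5.1.1, 7.2 and 8.2 so that one stated rule, of its own choosing, governs the ROAT zone when erythema appears. The text should give the scope of an interruption and say when the alternative arm site may be used. This review takes no position on what the rule should be.
- **Data collection.** Record the number of ROAT applications and the date and reason for any early stop or site change, drawing on the diary.
- **SAP 11.6.** Report the worst ROAT grade by arm, with a separate row for ROAT stopped early because of a local reaction.
- **DSMB.** Include that row in the data the board receives.
- **Notation.** Section 5.1.1 writes '1+' where Table 8.2 has '+'; align the two in the same edit.

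The cost is a protocol clarification, one eCRF field and one table row. The local-tolerance figures may look slightly less favourable.
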